9.1.11 ECG Procedure

A standard 12-lead ECG will be recorded. The investigator (or a qualified observer at the study site) will interpret the ECG using 1 of the following categories: within normal limits, abnormal but not clinically significant, or abnormal and clinically significant. The time that the ECG was performed will be recorded.

9.1.12 PK Sample Collection

9.1.12.1 Collection of Blood for PK Sampling

Blood samples (one 6-mL sample per scheduled time) for the determination of alogliptin, pioglitazone, and potential pioglitazone M-IV metabolite plasma concentrations will be collected into chilled vacutainers containing anticoagulant potassium ethylenediamine tetra-acetic acid (K₂EDTA) according to the schedule in [Appendix A](#). Instructions for sample processing and shipment are provided in [Appendix E](#).

Serial blood samples for determination of alogliptin and pioglitazone will be collected according to [Table 9.b](#).

Table 9.b Collection of Blood Samples for PK Analysis

Analyte	Matrix	Dosing Day	Scheduled Time (hours)
Alogliptin	Plasma	1	Predose (within 15 minutes prior to dose) and 0.25, 0.5, 1, 1.5, 2, 3, 4, 6, 8, 12, 16, 24, 36, 48, and 72 hours postdose
Pioglitazone and (potential) pioglitazone M-IV metabolite	Plasma	1	Predose (within 15 minutes prior to dose) and 0.25, 0.5, 1, 1.5, 2, 3, 4, 6, 8, 12, 16, 24, 36, 48, and 72 hours postdose

The actual time of sample collection will be recorded on the source document and eCRF.

Note that bioanalytical data for pioglitazone M-IV metabolite will be collected and stored for possible future use but that plasma concentrations will not be calculated or reported at this time.

9.1.12.2 Bioanalytical Methods

Plasma concentrations of alogliptin will be measured using a validated high-performance liquid chromatography with tandem mass spectrometry method. Plasma concentrations of pioglitazone will be measured using a validated high-performance liquid chromatography with tandem mass spectrometry method.

9.1.13 PK Parameters

The PK parameters of alogliptin and pioglitazone will be determined from the concentration-time profiles for all evaluable subjects. Actual sampling times, rather than scheduled sampling times, will be used in all computations involving sampling times. The following PK parameters will be calculated for plasma concentration values of alogliptin and pioglitazone:

Symbol/Term	Definition
Plasma	
AUC_{72}	Area under the concentration-time curve from the time 0 to time 72 hours.
AUC_t	Area under the concentration-time curve from time 0 to time t.
CCI	
C_{max}	Maximum observed concentration.
CL/F	Apparent clearance after extravascular administration, calculated using the observed value of the last quantifiable concentration.
λ_z	Terminal disposition phase rate constant.
$t_{1/2z}$	Terminal disposition phase half-life.
t_{max}	Time of first occurrence of C_{max} .

9.1.14 Documentation of Screen Failure

Investigators must account for all subjects who sign informed consent. If a subject is withdrawn at the screening visit, the investigator should complete the eCRF screen failure form.

The primary reason for screen failure is recorded in the eCRF using the following categories:

- Predose event/AE.
- Did not meet inclusion criteria or did meet exclusion criteria <specify reason>.
- Significant protocol deviation.
- Lost to follow-up.
- Voluntary withdrawal <specify reason>.
- Study termination.
- Other <specify reason>.

Subject identification numbers assigned to subjects who fail screening should not be reused.

9.1.15 Documentation of Randomization

Only subjects who meet all of the inclusion criteria and none of the exclusion criteria are eligible for randomization into the dosing phase.

If the subject is found to be not eligible for randomization, the investigator should record the primary reason for failure on the applicable eCRF.

9.2 Monitoring Subject Dosing Compliance

Study medication will be administered while subjects are under observation in the clinical research unit. Following administration of the study drug, appropriate mouth and/or hand checks will be performed to ensure that the dose is swallowed and noted in the source document. The date and time of each dose will be recorded in the source documents and on the eCRFs. An inventory of the study drug supplies dispensed will be performed by the site pharmacist or authorized study designee and recorded onto the Drug Accountability Log in the subject's source document records or equivalent. The exact dose time of consecutive subjects may be staggered to facilitate logistics at the site.

9.3 Schedule of Observations and Procedures

The schedule for all study-related procedures for all evaluations is shown in [Appendix A](#). Assessments should be completed at the designated visit/time point(s).

9.3.1 Screening

Subjects will be screened within 28 days prior to randomization. Screening may consist of 1 or more visits. Subjects will sign an informed consent form at the first visit and return to the clinic in a fasted state for safety laboratory testing at the second visit. Subjects will be screened in accordance with predefined inclusion and exclusion criteria as described in Section 7.0. A screen failure rate of approximately 50% is anticipated. Therefore, an estimated 144 subjects will be screened in order to enroll 72 subjects. See Section 9.1.14 for procedures for documenting screening failures.

9.3.2 Study Randomization

Study randomization will take place on Day 1 of Period 1.

If the subject has satisfied all of the inclusion criteria and none of the exclusion criteria for randomization, the subject should be randomized as described in Section 8.2. Subjects will be administered the first dose of test or reference drug in the unit under the supervision of the investigator or designee, as described in Section 8.2. The procedure for documenting Screening failures is provided in Section 9.1.14.

9.3.3 Drug Intake/Washout Period

Subjects will be confined to the clinic from Check-in (Day -1) of Dosing Period 1 until the 24-hour blood sample has been collected on Day 2 of Dosing Period 1 and from Day 7 of Dosing Periods 1,

2, and 3 until the 24-hour blood sample has been collected on Day 2 of Dosing Periods 2, 3, and 4, respectively. Subjects will be discharged or released from the unit unless deemed inappropriate by the investigator because of safety concerns. Subjects will return to the clinic for the 36-hour blood sample collection on Day 2 and on Days 3 and 4 of each period to complete study procedures.

There is a 7-day washout interval between the dose in each period.

The study consists of a Screening Period (Days -28 to Day-2) and 4 Drug Intake Periods. A washout interval of 7 days (beginning immediately after dosing on Day 1 of Period 1) will separate the doses of each study period. Subjects will be admitted into the clinic on Day -1 (at least 10 hours prior to study drug administration), will be dosed on Day 1 and discharged from the clinic after the 24-hour blood sample has been collected on Day 2 of each period. Blood samples for determination of alogliptin and pioglitazone plasma concentrations will be collected prior to dosing on Day 1 through 72 hours postdose.

9.3.4 Final Visit/ Early Termination

If a subject discontinues, the reason for discontinuation must be documented in the source document and eCRF. The PK sample collection should be collected at the Early Termination Visit, if possible and relatively close to a protocol-specified time point. The site may seek guidance. For example, collect samples if early withdrawal is due to an AE, and/or if several hours elapsed since last blood draw.

Final Visit procedures will be performed on Day 4 of Period 4.

For all subjects receiving study drug, the investigator must complete the End of Study eCRF page.

9.3.5 Follow-Up Visit/Telephone Call

At 14 days \pm 2 days following the last dose of study drug a Follow-up telephone call will be made by the site to inquire for any ongoing AEs or SAEs, new AEs or SAEs, and concomitant medications taken since final dose of study medication. Subject who withdrew consent should still be contacted for a safety Follow-up telephone call, but the contact should only be recorded in the medical records and not in the eCRF, according to data protection regulations.

9.4 Blood Volume

Total blood sampling volume for an individual subject is shown in [Table 9.c](#)

Table 9.c Approximate Blood Volume

Sample Type	Sample Volume (mL)	Number of Samples					Total Volume (mL)
		Screening	Period 1	Period 2	Period 3	Period 4	
Clinical laboratory test samples	10 (a)	1	1	0	0	1	33
PK samples alogliptin and pioglitazone	6	-	16	16	16	16	384 (b)
Total Approximate Blood Sampling Volume							417

(a) The sample volume at Screening will be 13 mL.

(b) Additionally, up to 52 mL of blood will be discarded at time points when blood is drawn using a catheter.

The approximate total volume of blood collected from one subject for the study is 469 mL.

Blood samples for PK analysis will be collected via venous catheter through the 24-hour postdose PK sample in each period. With use of a peripheral venous catheter, the catheter will be irrigated with 0.5 mL heparinized saline solution (500 ME per 100 mL of 0.9% NaCl) after each blood sampling or after the catheter is inserted, in order to avoid catheter thrombosis. In addition, prior to taking each PK blood sample from the catheter, 1 mL blood will be drawn and discarded, in order to take into account the holdup volume (approximately 0.1 mL) within the catheter. Blood samples will be collected via venipuncture in cases of catheter thrombosis and for outpatient blood sampling at 36, 48, and 72 hours postdose.

10.0 PREDOSE EVENTS AND ADVERSE EVENTS

10.1 Definitions

10.1.1 Predose AEs

A predose AE is defined as any untoward medical occurrence in a clinical investigation subject who has signed informed consent to participate in a study but prior to administration of any study medication. Any AE, including abnormalities in laboratory, ECG, vital signs, or physical examination, will exclude the subject from participating in this clinical study.

10.1.2 AEs

An AE is defined as any untoward medical occurrence in a clinical investigation subject administered a drug; it does not necessarily have to have a causal relationship with this dosing.

An AE can therefore be any unfavorable and unintended sign (eg, abnormal laboratory value), symptom, or disease temporally associated with the use of a drug whether or not it is considered related to the drug.

10.1.3 Additional Points to Consider for AEs

An untoward finding generally may:

- Indicate a new diagnosis.
- Necessitate therapeutic intervention.
- Require an invasive diagnostic procedure.
- Require discontinuation or a change in dose of study drug or a concomitant medication.
- Be considered unfavorable by the investigator for any reason.

AEs caused by a study procedure (eg, a bruise after blood draw) should be recorded as an AE.

Diagnoses vs signs and symptoms:

- Each event should be recorded to represent a single diagnosis. Accompanying signs (including abnormal laboratory values or ECG findings) or symptoms should NOT be recorded as additional AEs. If a diagnosis is unknown, sign(s) or symptom(s) should be recorded appropriately as an AE(s).

Laboratory values and ECG findings:

- Changes in laboratory values or ECG findings are considered to be AEs. Repeated or additional noninvasive testing for verification, evaluation or monitoring of an abnormality is allowed.
- If abnormal laboratory values or ECG findings are the result of pathology for which there is an overall diagnosis (eg, increased creatinine in renal failure), the diagnosis only should be reported appropriately as an AE.

Pre-existing conditions:

- Subjects with pre-existing medical conditions will not be enrolled to this study.

Worsening of AEs:

- If the subject experiences a worsening or complication of an AE, the worsening or complication should be recorded as a new AE. Investigators should ensure that the AE term recorded captures the change in the condition (eg, “worsening of...”).

Changes in intensity of AEs:

- If the subject experiences changes in intensity of an AE, the event should be captured once with the maximum intensity recorded.

Elective surgeries or procedures:

- Elective surgeries or procedures are not permitted during the trial; should they be required, the subject will be withdrawn.

Overdose:

- Cases of overdose with any medication without manifested side effects are NOT considered AEs, but instead will be documented on an Overdose page of the eCRF. Any manifested side effects will be considered AEs and will be recorded on the AE page of the eCRF.

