6.0 STUDY DESIGN AND DESCRIPTION

6.1 Study Design

This is a single-center, open-label, randomized, 4-sequence, 4-period, single dose crossover study involving 72 healthy adult, male and female subjects between the ages of 18 and 55 years, inclusive.

Subjects will be randomized in the order in which they are enrolled into the study. The 72 eligible subjects will be randomized to 1 of 4 drug intake sequences in a 1:1:1:1 ratio. Due to the large sample size, volunteers may be divided into 2 or 3 cohorts according to space limitations at the site. All cohorts will be dosed sequentially.

The study consists of a Screening Period (Days -28 to Day-2) and 4 Drug Intake Periods. A washout interval of 7 days (beginning immediately after dosing on Day 1) will separate the doses of each study period. Subjects will be admitted into the clinic on Day -1 (Day 7 of the preceding period for Periods 2, 3, and 4) and will be dosed on Day 1 of each period. Starting on Day 1 of each period, blood samples for determination of alogliptin and pioglitazone plasma concentrations will be collected predose through 72 hours postdose. The subjects will be discharged from the clinic after the 24-hour blood sample collection on Day 2 of each period and will return to the clinic for the 36-hour blood sample collection on Day 2 and on Days 3 and 4 of each period to complete study procedures. Final Visit procedures will be performed on Day 4 of Period 4 and a Follow-up call will be made 14 days \pm 2 days following the last dose of study drug.

A schematic of the study design is included as [Figure 6.a](#). A schedule of assessments is listed in [Appendix A](#).

Figure 6.a Schematic of Study Design

Predose Period			Drug Intake Period (c)								
Screening (a)	Check-in (b)		Period 1		Period 2		Period 3		Period 4		
Days -28 to -2	Day -1		Day 1 Dosing	Days 2 to at least 7	Day 1 Dosing	Days 2 to at least 7	Day 1 Dosing	Days 2 to at least 7	Day 1 (d) Dosing	Days 2 to 3	Day 4 Final Visit/ET
		Sequence I (n=18)	A	WO	B	WO	C	WO	D	WO	
		Sequence II (n=18)	B		C		D		A		
		Sequence III (n=18)	C		D		A		B		
		Sequence IV (n=18)	D		A		B		C		

A=SYR-322-4833 BL (25 mg + 15 mg) (test regimen), B=alogliptin 25 mg + pioglitazone 15 mg (reference regimen), C=SYR-322-4833 BL (25 mg + 30 mg) (test regimen), D=alogliptin 25 mg + pioglitazone 30 mg (reference regimen), ET=Early Termination, WO=Washout of 7 days between dosing.

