10.1.9 Start Date

The start date of the AE is the date that the first signs/symptoms were noted by the subject and/or investigator.

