7.11.1 Adverse Events

A treatment-emergent adverse event (TEAE) is defined as an adverse event (AE) or serious adverse event (SAE) that started or worsened after first study drug administration and within 14 days (30 days if SAE) of last dose of study drug (onset date – date of last dose + 1 ≤ 14), see Protocol Section 10.2.1.1. A TEAE will be attributed to a regimen if the TEAE occurs after administration of the study drug in a period and up to just prior to study drug administration in the next period. A TEAE that occurs after administration of the study drug in the last period and up to 14 days after the last study drug dose is attributed to the regimen received in the last period. All AE verbatim terms will be coded by system organ class (SOC) and preferred term using (PT) the MedDRA coding system. Any subject that doesn't not complete all 4 regimens/periods will be included in the AE summaries, and will be included in each of the regimens for which they

were treated and any AEs happening after their last regimen exposure (inclusive of 30 days) will be included in the tally of that regimen.

TEAEs will be summarized by regimen and overall. The tables will include the number and percentage (N [%]) of subjects reporting any event for that term. The denominator, within a regimen summary, will be the total number of subjects that received the regimen.

The following TEAE tables will be summarized by part.

- Overview of TEAEs.
- TEAEs by SOC and PT.
- Most Frequent TEAEs by PT term
- Most Frequent Non-Serious TEAEs by PT
- Relationship of TEAEs to Study Drug by SOC and PT.
- Study Drug-Related TEAEs by SOC and PT.
- Severity of TEAEs by SOC and PT.
- Severity of Drug-Related TEAEs by SOC and PT.

In addition, pretreatment events (PTEs) will be summarized overall by SOC and PT.

For each regimen and overall, subjects reporting more than one occurrence for a term (SOC or PT) being summarized will be counted only once using the most extreme incident (most severe for the severity tables and related for the relationship to study drug tables).

Most frequent TEAEs are those events occurred in at least $\geq 5\%$ (before any rounding) of subjects in a regimen.

Data listings will be provided for all TEAEs, PTEs, TEAEs that led to study discontinuation, TEAEs that led to abnormal liver functions, SAEs, AEs that resulted in death, and AEs occurring more than 30 days after the last dose of study medication.

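### Protocol 10.1.3 gives two conflicting recording rules for an AE that increases in intensity; the capture-once rule, applied across a dosing day, puts the worst grade under the earlier regimen

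*Protocol*

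**What the plan says.** Protocol 10.1.3 (Additional Points to Consider for AEs) has two consecutive items.

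- On worsening: "If the subject experiences a worsening or complication of an AE, the worsening or complication should be recorded as a new AE". It adds: "Investigators should ensure that the AE term recorded captures the change in the condition".
- On changes in intensity: "If the subject experiences changes in intensity of an AE, the event should be captured once with the maximum intensity recorded".

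Protocol 10.1.9 fixes the date of each record: "The start date of the AE is the date that the first signs/symptoms were noted by the subject and/or investigator". Protocol 10.2.1.2 lists what is documented for each event. The list includes start and stop dates and intensity, but no date on which intensity changed.

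SAP 7.11.1 defines a treatment-emergent AE as one "that started or worsened after first study drug administration", within a window after the last dose. It assigns events to regimens as follows: "A TEAE will be attributed to a regimen if the TEAE occurs after administration of the study drug in a period", up to just before the next period's dose. Doses are a week apart (Protocol 6.1): "A washout interval of 7 days (beginning immediately after dosing on Day 1) will separate the doses of each study period".

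**The concern.** An AE that goes from mild to severe is both a worsening and a change in intensity, so a site can follow either item and believe it has complied. The two choices produce different data. The first gives two records, the second dated at the increase. The second gives one record with the original start date and the worst grade.

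Where treatment does not change, this affects only the number of records. Here treatment changes every 7 days, so the start date of the record decides which regimen is charged with the event. The AE comparison of FDC with coadministration is a stated additional objective (Protocol 5.1.2, SAP 4.3), and it rests on the by-regimen incidence and severity tables. A recording choice made at the site could therefore move a grade from one side of that comparison to the other.

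**Working it through.** The plan gives no figure to reproduce. The check is to trace one event through the rules and then through the sequences.

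**Step 1: one event, two recording rules.** Take a Sequence I subject (A, then B). A mild headache starts late in Period 1 and becomes severe after the Period 2 dose.

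| | Worsening rule | Capture-once rule |
|---|---|---|
| Records | Mild, dated in Period 1; severe, dated in Period 2 | One, severe, dated in Period 1 |
| Regimen A (Period 1) | One subject, mild | One subject, severe |
| Regimen B (Period 2) | One subject, severe | None, unless the subject has another event of that term in Period 2 |

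Under capture-once, the incidence for A is correct, because the headache did start there; only its grade is too high. Regimen B loses the event. If the subject has a separate event of the same term under B, the incidence cell for B does not change, because SAP 7.11.1 counts a subject once per term within a regimen.

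**Step 2: whether the SAP corrects this.** The SAP attributes an event by when it occurs and does not define that word for an event that changes grade. Two passages point to the onset date. The treatment-emergent window in 7.11.1 is computed from onset, and the missing-date conventions in 7.1.4 place an event by onset, or by stop date if onset is missing. Worsening appears in the definition only relative to the first dose. Protocol 10.1.1 excludes a subject with any predose AE, so worsening of a predose event should hardly arise. Worsening across the doses of Periods 2, 3 and 4 can arise and has no rule. The listed AE fields do not hold the date of the increase, so the analysis cannot recover it from them.

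**Step 3: direction of the shift.** The sequences are ABCD, BCDA, CDAB and DABC (Protocol Figure 6.a), giving 4 × 3 = 12 within-study transitions.

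| Transition | Sequences | A worsening under | Is tabulated under |
|---|---|---|---|
| A to B | I, III, IV | B (coadministration) | A (FDC, same strength) |
| B to C | I, II, IV | C (FDC) | B (coadministration, other strength) |
| C to D | I, II, III | D (coadministration) | C (FDC, same strength) |
| D to A | II, III, IV | A (FDC) | D (coadministration, other strength) |

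All 12 transitions cross between FDC and coadministration. A worsening under B or D moves to its own comparator, A or C. Six transitions move a grade from coadministration to FDC and six the other way.

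**Step 4: size of one case.** The denominator is the number of subjects who received the regimen, at most 72. One subject is 1/72 = 1.4 percentage points. If the planned 14% drop-out left 72 × 0.86 ≈ 62 subjects on a regimen, it would be 1/62 = 1.6 points.

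**The case against.** The strongest reply is that the protocol already handles the case. The worsening item stands directly above the intensity item, calls for a new AE and asks for a term that shows the change. A new record has its own start date, and the SAP would place it under the later regimen. On that reading attribution is correct, and much of the remedy already exists. This stands against the inference that the protocol instructs sites to count every worsened AE under the previous regimen. It does not; the misplacement occurs only where a site applies the capture-once item.

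It does not remove the conflict. The intensity item is unqualified and literally describes a rise from mild to severe. One could reconcile the two by reading worsening as a change in the nature of the condition. A pure rise in grade then falls under capture-once, which is the reading that misattributes.

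Two other inferences are tempting. One is that both regimens get wrong incidence counts. Step 1 shows that the earlier regimen's incidence is right and only its grade is inflated. The other is that the error favours one formulation overall. The effect within a strength is not balanced, but across all four regimens the transitions run equally in both directions.

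The objection on importance largely stands. A case needs an AE still ongoing 7 days after a single dose in healthy subjects, which then intensifies after the next dose and is recorded under the capture-once item. Protocol 9.1.6 also excludes subjects who take any concomitant medication. AEs are summarised descriptively with no hypothesis test. The AE listings, with start and stop dates, would show which events span a dosing day, though not when the grade changed.

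**Conclusion.** The point holds as a conflict between two recording rules, one of which misattributes severity in this crossover. It rests on two conditions: that a site applies the capture-once item to an increase after a later dose, and that the SAP attributes by the record's onset date, which its window formula and missing-date conventions imply but do not state for this case.

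Where both hold, the earlier regimen shows too high a grade with the correct incidence, and the later regimen omits the worsening unless it has another event of that term. Each affected cell moves by about 1.4 percentage points. The number of cases cannot be estimated from the documents and is probably small. The consequence is confined to the by-regimen AE tables. Cmax, AUC72 and the bioequivalence conclusion are unaffected. Severity: minor.

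**What to change.** - **Protocol 10.1.3 and the eCRF completion guidance:** limit the capture-once item to changes in intensity within one dosing period. State that an increase in intensity after a later period's dose falls under the existing worsening item and is recorded as a new AE dated at the increase.
- **SAP 7.11.1:** state that a worsened event is attributed to the regimen in effect on the date of worsening.

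The cost is about one sentence in each document, with no new assessments. The downside is an occasional extra AE record. It would not inflate the tables if it codes to the same term, since subjects are counted once per term within each regimen and overall. The wording has to reach the site before AEs are entered, because the listed fields do not allow the date of the increase to be rebuilt at analysis.
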